10.4 Vital signs, physical findings, and other observations related to safety

10.4.1 Vital Signs

Vital measurements (including SBP, DBP, PR, RR and weight) are generally collected in standard units. If any measurements are collected in international units, they will be converted to standard units for summaries. Subject Listings will be prepared for vitals variables.

The observed value and change from Baseline will be summarized descriptively by treatment group and scheduled study visit. In the same table, the observed value and change from Baseline will be summarized by treatment for all scheduled visits. The Last Visit, minimum, and maximum post-baseline values during the Treatment Period will also be included.

The number and percentages of subjects with abnormal vital signs and body weight during the Treatment Period will be presented by treatment group and PSL total group. The abnormal vital sign and body weight criteria are provided in Appendix 13.2. Subject numbers for those meeting abnormal criteria will also be presented.

10.4.2 Electrocardiograms

ECG parameters include heart rate, PR interval, QRS duration, QT interval, QTcB [QT corrected for heart rate using Bazett's formula], and QTcF [QT corrected for heart rate using Fridericia's formula].

The observed ECG parameter values and their change from Baseline will be summarized (SS) descriptively by treatment group and PSL total group for each scheduled assessment visit. The Last Visit, minimum, and maximum post-baseline values during the Treatment Period will also be included. In addition, the number and percentage of subjects with QTc (Bazett and Fridericia corrected) classifications of <450ms, 450 to <480ms, 480 to <500ms, and ≥ 500 ms and change from baseline of <30ms, 30 to <60ms, and ≥ 60 ms will be presented for each visit.

For each ECG, the overall ECG result, is also collected, categorized as one of: no abnormality, an abnormal but not clinically significant finding, or a clinically significant finding. The number and percentage of subjects with no abnormality, an abnormal but not clinically significant finding, and a clinically significant finding will be summarized for each of the scheduled assessment visits. Percentages for the visit will be relative to the number of subjects with an ECG result for the visit.

The number and percentages of subjects with abnormal ECG during the Treatment Period will be presented by treatment group and PSL total group. The abnormal ECG criteria are provided in Appendix 13.3. Subject numbers for those meeting abnormal criteria will also be presented.

10.4.3 Echocardiograms

Echocardiogram data are collected at Visit 1, Visit 6, and Visit 9. Depending on the availability of data, echocardiogram abnormalities (Left Ventricle, Left Atrium, Right Ventricle, Right Atrium, Pericardium, Pulmonary Artery Systolic Pressure and overall assessment) will be summarized by treatment group and PSL total group and scheduled visit as the number and percentage of subjects with an abnormality. In addition, Echocardiogram Valvular abnormality grade (Aortic Valve, Mitral Valve, Tricuspid Valve, Pulmonary Valve) described in Appendix 13.4 will be summarized descriptively. Valvular abnormality grade equal or larger than grade 2 is corresponding to valvular abnormal. Subject numbers with abnormality for any assessment will be provided.

10.4.4 Other safety variable(s)

10.4.4.1 Physical Examination

Data from the Physical Examination are only provided in subject data listings presented by treatment group, subject and visit, displaying all data collected for all subjects. No summaries will be provided. Findings that are considered clinically significant will be reported AEs.

10.4.4.2 Neurologic Examination Data

Data from the Neurological Examination are collected on the Neurological Examination Complete and Neurological Examination Brief CRFs and are not summarized. Data from the Neurological Examination are only provided in subject data listings presented by treatment group, subject and visit, displaying all data collected for all subjects. No summaries will be provided. Findings that are considered clinically significant will be reported as AEs.

10.4.4.3 Psychiatric and Mental Status Data

The Psychiatric and Mental Status assessment is performed at Baseline and all scheduled visits. These data are collected on the Psychiatric and Mental Status CRF. Assessment of specific domains of psychiatric and cognitive symptoms will be performed by a staff member trained in the identification of psychiatric symptoms. The parameters that evaluated are orientation, attention, memory, mood, and calculus. These parameters will be assessed as normal or abnormal and then determined whether clinically significant. The presence of psychiatric symptoms, mental impairment, or behavioral problems are also assessed and evaluated as normal or abnormal, and whether they are clinically significant.

For each of these assessments, the number and percentage of subjects with an abnormal result, and the number and percentage with an abnormal result considered clinically significant, will be summarized at each scheduled visit.

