### **4.2.2 Other safety variables**

Other safety variables are as follows:

- Incidence of TEAEs reported by the subject and/or caregiver or observed by the Investigator during the following periods: 16-week Treatment Period, 12-week Maintenance Period, 4-week Titration/Stabilization Period, and 3-week Taper Period
- Number of and reason for subjects requiring premature tapering due to TEAEs
- Number of and reason for subjects requiring a dose reduction during the Stabilization Period due to TEAEs
- Incidence of treatment-emergent SAEs during the following periods: 16-week Treatment Period, 12-week Maintenance Period, 4-week Titration/Stabilization Period
- Changes in clinical laboratory test parameters (including hematology, blood chemistry, and urinalysis)
- Changes in vital sign parameters (including pulse rate, SBP, DBP, and respiratory rate)
- Changes in 12-lead ECG parameters
- Physical examination (including body weight) and neurological examination findings
- Changes in Psychiatric and Mental Status exam
- Occurrence of valvular abnormalities or pericardial effusion changes or other significant abnormalities as identified by 2-dimensional Doppler echocardiogram at each assessment by central reader
- Changes in withdrawal symptoms using Clinical Institute Withdrawal Assessment-Benzodiazepines (CIWA-B) from the end of the 16-week Treatment Period (Visit 7) to the end of the Taper Period (Visit 8) and the end of the SFU Period (Visit 9 [30 days after the last IMP intake])

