### **11.7.7 Psychiatric and mental status**

The psychiatric and mental status of subjects will be closely monitored. Assessment of specific domains of psychiatric and cognitive symptoms will be performed by a staff member trained in the identification of psychiatric symptoms. The Psychiatric and Mental Status assessment will be performed at Baseline and all scheduled visits ([Table 5-1](#)). The parameters that will be evaluated are orientation, attention, memory, mood, calculus, behavior, and thinking or feeling. These parameters will be assessed as normal or abnormal and then determined whether clinically significant. In addition, if present and abnormal, psychiatric symptoms, mental impairment, and behavioral problems will be assessed as to whether they are clinically significant.

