2.3.2 Other safety variables

Other safety variables are as follows:

- Incidence of TEAEs reported by the subject and/or caregiver or observed by the Investigator during the following periods: 16-week Treatment Period, 12-week Maintenance Period, 4-week Titration/Stabilization Period, and 3-week Taper Period
- Number of and reason for subjects requiring premature tapering due to TEAEs
- Number of and reason for subjects requiring a dose reduction during the Stabilization Period due to TEAEs
- Incidence of treatment-emergent SAEs during the following periods: 16-week Treatment Period, 12-week Maintenance Period, 4-week Titration/Stabilization Period
- Changes in clinical laboratory test parameters (including hematology, blood chemistry, and urinalysis)
- Changes in vital sign parameters (including pulse rate, systolic BP, diastolic BP, and respiratory rate)
- Changes in 12-lead ECG parameters

- Physical examination (including body weight) and neurological examination findings
- Changes in Psychiatric and Mental Status
- Occurrence of valvular abnormalities or pericardial effusion changes or other significant abnormalities as identified by 2-dimensional Doppler echocardiogram at each assessment by central reader
- Changes in withdrawal symptoms using Clinical Institute Withdrawal Assessment-Benzodiazepines (CIWA-B) from the End of Treatment Visit (Visit 7) to end of the Taper Period (Visit 8) and end of the SFU Period (Visit 9 [30 days after the last IMP intake]).

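### Psychiatric and Mental Status is named as a change, but the SAP tabulates only by-visit abnormality, and its parameter list omits two of the protocol's seven parameters

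*SAP*

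**What the plan says.** **The variable.** Protocol 4.2.2 lists "Changes in Psychiatric and Mental Status exam" among the other safety variables, and SAP 2.3.2 lists "Changes in Psychiatric and Mental Status". Neither section names parameters.

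**The parameters.** Protocol 11.7.7 states: "The parameters that will be evaluated are orientation, attention, memory, mood, calculus, behavior, and thinking or feeling". Each is rated normal or abnormal and then for clinical significance. It adds that, "if present and abnormal, psychiatric symptoms, mental impairment, and behavioral problems will be assessed as to whether they are clinically significant". SAP 10.4.4.3 states "The parameters that evaluated are orientation, attention, memory, mood, and calculus", and then "The presence of psychiatric symptoms, mental impairment, or behavioral problems are also assessed and evaluated as normal or abnormal".

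**The tabulation.** SAP 10.4.4.3 plans this: "For each of these assessments, the number and percentage of subjects with an abnormal result". A second count is limited to abnormal findings judged clinically significant. Both are tied to the visit schedule, and the section specifies no other output. SAP section 10 adds that safety data are shown for each arm and for PSL total.

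**Related rules.** Protocol 13.4.1 planned only listings for this assessment. SAP 3.1 leaves unscheduled visits out of by-visit summaries, but lets them count towards the Last Visit value. SAP 3.2.5 puts a Last Visit row into by-visit summaries unless noted otherwise.

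**The concern.** A by-visit percentage of abnormal results answers a different question from a change. A subject whose memory or mood was already abnormal before dosing counts the same as one who becomes abnormal on drug. Subjects with drug-resistant epilepsy may well have such findings before dosing, although the documents give no rate. The question matters because acute psychiatric effects are a recognised risk of PSL. Protocol 2.3.1 reports three subjects who needed psychiatric admission, Protocol 6.3 criterion 10 ties withdrawal to clinically concerning psychiatric or behavioral disturbance, and Protocol 13.7 asks the DMC to watch behavioral events.

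The parameter list raises a second, smaller question. If the tables follow the SAP list, a finding recorded under one of the two unnamed parameters has no row of its own.

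**Working it through.** **1. Item lists side by side.** Protocol 11.7.7 has 7 parameters plus 3 further items. SAP 10.4.4.3 has 5 parameters plus the same 3 items, so 5 + 3 = 8 items are tabulated. The two protocol parameters missing by name are behavior and thinking or feeling. The item on behavioral problems partly covers the first. The second has no named counterpart and could only fall under psychiatric symptoms. SAP 3.9, which sets out changes from the protocol, is silent on this.

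**2. Comparison with the SAP's other safety sections.** The SAP uses the subject's own Baseline elsewhere:
- SAP 10.3 has shift tables for hematology and chemistry, and counts possibly clinically significant laboratory values at any scheduled or unscheduled visit in the Treatment Period.
- SAP 14.2 defines low pulse and blood pressure in adults partly by the fall from Baseline.
- SAP 14.4 defines treatment-emergent for ECG as met after Baseline, unscheduled visits included, and not met at Baseline.

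SAP 10.4.4.3 has no equivalent.

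**3. What the by-visit layout can miss.** An abnormality found at an unscheduled visit, and normal again at a later assessment, enters no scheduled-visit row and is not the Last Visit value. For the EDV, SAP 3.2.4 maps in-clinic safety assessments to the next scheduled visit and leaves others unmapped. It gives examples of each but does not say where the psychiatric assessment belongs. The Last Visit row would normally hold an EDV finding, but it still shows prevalence.

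**4. Illustration of the mixing.** There is no stated figure to reproduce, and the rates below are assumptions. Let b be the proportion abnormal at Baseline, i the proportion of Baseline-normal subjects who become abnormal (5% placebo, 15% PSL, a ratio of 3.0), and r the proportion of Baseline abnormalities that resolve, equal in both arms. By-visit prevalence is

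p = b(1 − r) + (1 − b)i.

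| b | r = 0: placebo vs PSL | Ratio | r = 0.5: placebo vs PSL | Ratio |
|---|---|---|---|---|
| 5% | 9.75% vs 19.25% | 1.97 | 7.25% vs 16.75% | 2.31 |
| 20% | 24% vs 32% | 1.33 | 14% vs 22% | 1.57 |
| 40% | 43% vs 49% | 1.14 | 23% vs 29% | 1.26 |

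Example for b = 40%, r = 0: 0.40 + 0.60 × 0.05 = 0.43 and 0.40 + 0.60 × 0.15 = 0.49. The difference between arms is (1 − b) × 10 points, so 9.5, 8 and 6 points. A table restricted to subjects normal at Baseline shows 5% vs 15% in every row.

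**5. Does the Baseline column repair this?** If nothing resolves, yes in aggregate: at b = 40% the rises are 43 − 40 = 3 and 49 − 40 = 9 points, a ratio of 3.0. If half resolve, the changes are 23 − 40 = −17 and 29 − 40 = −11 points. Both arms then fall although 5% and 15% of Baseline-normal subjects became abnormal. Net change equals new onset only when nothing resolves.

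The table also assumes that each new abnormality is still present at the visit shown. Protocol 2.3.1 calls the acute psychiatric events transient, so a single-visit row could hold fewer.

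**The case against.** The case against has weight, and several parts of it stand.

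- The SAP does more than the protocol asked. Protocol 13.4.1 planned listings only, so the by-visit table is an addition and not a weakened analysis.
- The named risk has another route. SAP 10.2 tabulates TEAEs by SOC and PT, serious TEAEs and TEAEs leading to discontinuation, and TEAEs are new or worsened by definition. A psychiatric admission meets the SAE definition in Protocol 11.1.1.2. Protocol 11.7.4 includes mental status in the physical examination and records clinically significant changes since Baseline as AEs. However, SAP 10.4.4.1 and 10.4.4.2 state that clinically significant findings become AEs, whereas SAP 10.4.4.3 does not say so for this assessment.
- The table has a Baseline value, a placebo arm and, by default, a Last Visit row. These allow a comparison of groups, with the limit shown in step 5.
- The CRF is not among the documents. The two unnamed parameters may be collected under other headings, or not separately at all.

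A reader might infer that only five domains are tabulated, or that new psychiatric effects go uncounted. The text does not support this: eight items are summarized, a new abnormality present at a scheduled visit counts in that visit's row, and SAP 3.1 has all documented data listed. A reader might also take the seven parameters to be the SAP's own definition; that list is the protocol's. Nor can the illustration be turned into a loss of power, because SAP 10.4.4.3 plans counts and percentages and no test.

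**Conclusion.** The point holds in a limited form. A variable named as a change is summarized only as by-visit abnormality, without a within-subject comparison or an any-time-on-treatment count. The table therefore cannot separate new from pre-existing abnormality, and a finding confined to an unscheduled visit can be missed. Separately, two of the seven protocol parameters are absent by name, one of them partly covered by another item, and the difference is undeclared.

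The textual findings rest on no assumption. The size does: under the assumed 5% and 15%, a threefold ratio appears as 1.14 to 1.97 with no resolution, and as 1.26 to 2.31 if half of the Baseline abnormalities resolve, for 5% to 40% abnormal at Baseline. Any of these rates could be wrong. The ratios do not depend on the number of subjects, so early termination does not alter them. No efficacy conclusion is affected, and psychiatric TEAEs and SAEs remain tabulated. This is a worthwhile, inexpensive improvement to the description of a recognised risk.

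**What to change.** In SAP 10.4.4.3:

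1. Add one table, by arm and PSL total, giving for each item the number and percentage of subjects normal at Baseline who become abnormal, and who become abnormal and clinically significant, at any post-Baseline assessment in the Treatment Period. Include unscheduled visits and the EDV. Use subjects normal at Baseline as the denominator. Keep the by-visit table as support.
2. Align the parameter list with Protocol 11.7.7 as collected on the CRF. If behavior and thinking or feeling are recorded separately, give each a row. If they are recorded under another item, say which, and declare the difference in SAP 3.9.

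The cost is SAP wording and one more descriptive output. The new table needs no new data for the items already tabulated; rows for the two further parameters depend on the CRF. No test is needed.

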10.4.4.4 The Columbia-Suicide Severity Rating Scale (C-SSRS)

The C-SSRS questionnaire is self-administered by the subject and assessed by trained study personnel. This scale is used to assess suicidal ideation and behavior at Baseline (Visit 1), and at each subsequent study visit. C-SSRS data will be provided in subject listing for subjects with suicidal ideation and suicide behavior.

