Potential risks identified and relevant to clinical studies (cardiovascular events, psychiatric events, suicidal ideation and behavior [class risk], interactions with other medicinal products, pregnancy and lactation, worsening of seizures, substance abuse and dependence, and overdose) are all described in detail in Section 6.3 of the Investigator's Brochure and suggested lay language is provided to sites for study participants in the Informed Consent form (ICF). Reported acute psychiatric SAEs are consistent with adverse effects of other AEDs, including SV2A ligands. Although events were transient and acute, the occurrence of acute psychiatric effects in 3 study participants administered PSL in completed clinical studies required admission to psychiatric care and medical treatment. Therefore, the possibility of significant psychiatric adverse effects highlights the need to maintain vigilance for such effects. In view of the nonclinical histopathological cardiac findings of some minor asymptomatic, focal cardiac valvular, and epicardial inflammatory lesions in dogs, screening of study participants at Baseline and ongoing echocardiogram monitoring during treatment and post-treatment have been implemented as a precaution in the studies that have a  $>3$ -week treatment duration. To date, no

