#### **3.2 Secondary objective**

The secondary objective is to assess the safety and tolerability of PSL in relation to placebo.

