## **8.2 Treatment Period (16 weeks)**

### **8.2.1 Titration Period (3 weeks)**

#### **8.2.1.1 Visit 2, Baseline (Day 1, 4 weeks after Visit 1, $\pm 3$ days)**

The following procedures will be performed:

- Verify Inclusion and Exclusion criteria (including results of laboratory parameters, ECG, echocardiogram, and MRI obtained since Visit 1). In the event 1 of these results is not available, the visit may be delayed by 1 week.
- Verify withdrawal criteria
- Randomize subjects using IRT
- Obtain C-SSRS data since the last visit
- Obtain HADS data
- Obtain SSG data

- Obtain QOLIE-31-P data
- Measure vital signs (pulse rate, respiratory rate, SBP, and DBP), in supine position after 5 minutes of rest
- Measure body weight
- Perform brief physical examination (refer to Section 11.7.4 for details)
- Perform brief neurological examination (refer to Section 11.7.5 for details)
- Perform Psychiatric and Mental Status assessment
- Obtain 12-lead ECG
- Collect blood and urine samples for clinical laboratory analyses
- Collect blood sample for concomitant AED assay
- Perform urine pregnancy test (female subjects of childbearing potential only)
- Seizure evaluation (count and type) from subject's daily record card
- Record concomitant medications (AEDs and non-AEDs) and procedures
- Record AEs
- Record health-related outcomes and HRU (refer to Section 9.5 for details), with the exception of socio-professional status
- Dispense IMP using IRT

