## **13.4 Planned safety and other analyses**

### **13.4.1 Safety analyses**

Adverse events will be coded using the Medical Dictionary for Regulatory Activities (MedDRA®). Adverse events will be summarized by MedDRA System Organ Class and Preferred Term. The incidence of SAEs, AEs leading to premature discontinuation or dose tapering, and related AEs, and the incidence of AEs by maximum intensity, will also be summarized.

Laboratory values, ECG data (heart rate, PR interval, QRS duration, QT interval, QTcB or QTcF, and Investigator's conclusion on ECG profile) and arrhythmias, vital signs, weight, and changes from Baseline in these measures will be summarized by period, visit, and treatment group. Possibly clinically significant treatment-emergent abnormalities for laboratory values, vital signs, and weight will be listed and summarized by period and visit for each treatment group.

Electrocardiogram abnormalities as well as physical and neurological abnormalities will also be listed by period and visit. Quantitative safety parameters will be summarized descriptively by time point and treatment group. Categorical safety summaries will provide the number and percentage of subjects within each summarized category.

Doppler echocardiogram results at Baseline and during and after treatment, and changes from Baseline, will be listed and descriptively summarized.

All C-SSRS data obtained at Baseline and subsequent visits will be reported as a listing ordered by subject and visit. Psychiatric and Mental Status assessment and CIWA-B data will also be included using listings.

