3.3.2 Baseline for other variables

Unless otherwise specified, the last valid measurement before the first study medication administration will be used as the Baseline value, including the pre-dose assessments on the day of Visit 2. Unless otherwise stated, if a Baseline visit measurement is missing, and a Screening visit measurement is available, the most recent Screening value will be utilized as Baseline. Both

scheduled and unscheduled Screening visits will be considered. If a scheduled Baseline assessment is taken on the same day as first administration of study medication and no time is collected, it will be assumed to have been taken prior to study medication. The time point used for Baseline will be determined separately for each variable. An exception is blood pressure, where a complete set of both systolic and diastolic blood pressure should be selected for baseline. Baseline values for PK evaluations included in this SAP is defined in Section 9.

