16 ADDENDUM

All tables described in the SAP will be repeated for Japan and non-Japan subgroups.

This document cannot be used to support any marketing authorization application and any extensions or variations thereof.

REDACTED COPY

STATISTICAL ANALYSIS PLAN SIGNATURE PAGE

This document has been reviewed and approved per the Review and Approval of Clinical Documents Standard Operating Procedures. Signatures indicate that the final version of the Statistical Analysis Plan (SAP) or amended SAP is released for execution.

This document cannot be used to support any marketing authorization application and any extensions or variations thereof.

REDACTED COPY

Approval Signatures

Name: EP0092-SAP-Amend-1
Version: 1.0
Document Number: CLIN-000158296
Title: EP0092-SAP-Amend-1
Approved Date: 18 Aug 2020

Document Approvals	
Approval Verdict: Approved	Name: [REDACTED] Capacity: Clinical Date of Signature: 18-Aug-2020 07:23:45 GMT+0000
Approval Verdict: Approved	Name: [REDACTED] Capacity: Clinical Date of Signature: 18-Aug-2020 16:58:53 GMT+0000

This document cannot be used to support any marketing authorization application and any extensions or variations thereof.

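### Cheap improvement: the C-SSRS, the scale for a named class risk, gets only a subject listing, so lower-level ideation not reported as an adverse event is never tabulated against placebo

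*SAP*

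**What the plan says.** Protocol 2.4 lists "suicidal ideation and behavior [class risk"] among the potential risks relevant to the clinical studies. Protocol 3.2 states: "The secondary objective is to assess the safety and tolerability of PSL in relation to placebo".

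Protocol 11.7.6 makes the C-SSRS the instrument for suicidality, at screening and during the study. Protocol Table 5-1 schedules it at Visits 1 to 9, and Protocol 8.5 adds it at unscheduled visits made for safety or efficacy reasons.

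On output, Protocol 13.4.1 says: "All C-SSRS data obtained at Baseline and subsequent visits will be reported as a listing ordered by subject and visit". SAP 10.4.4.4 says: "C-SSRS data will be provided in subject listing for subjects with suicidal ideation and suicide behavior". No other SAP section, and no entry in its amendment log, plans a C-SSRS table. The scale is not in the safety variable lists (Protocol 4.2, SAP 2.3).

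SAP 16 adds: "All tables described in the SAP will be repeated for Japan and non-Japan subgroups".

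**The concern.** A listing does not compare arms. SAP 10.4.4.4 does not even say that the listing is grouped by treatment, as SAP 10.4.4.1 and 10.4.4.2 do for the physical and neurological examinations. A reader who wants to know whether ideation was more frequent on PSL than on placebo would have to count by hand, choosing a denominator and a time window after unblinding.

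The general sentence in SAP 10, that safety data are summarized by treatment group and PSL total, does not settle this. The specific text in 10.4.4.4 plans a listing and defines no summary.

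At stake is a modest loss of safety information on a risk that the sponsor has named. No efficacy conclusion is affected.

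**Working it through.** No planned figure bears on this point, so the check is mainly one of reading.

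**1. The three instruments that Protocol 13.4.1 leaves as listings**

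| Instrument | Protocol 13.4.1 | SAP |
|---|---|---|
| Psychiatric and Mental Status | listing | counts and percentages of abnormal and clinically significant results by visit (10.4.4.3) |
| CIWA-B (completed only by tapering subjects) | listing | listing plus a table of total scores (10.4.4.5) |
| C-SSRS | listing | listing only (10.4.4.4) |

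The SAP went beyond the protocol for two of the three. The C-SSRS text is not among the changes in SAP Amendment 1, so the missing table is not a cut made because of early termination.

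**2. What other outputs already capture**

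- Suicidality reported as an adverse event enters the TEAE and serious TEAE tables (SAP 10.2).
- Protocol 11.7.6 sends case details through SAE reporting. The sentence follows the text on a positive Question 4 and does not say which answers make a case.
- Withdrawal criterion 9 leaves withdrawal to the investigator's judgment on Question 4 and requires it on Question 5. Criterion 10 requires withdrawal for clinically concerning or worsening mood or behavioral disturbance. These subjects appear among the discontinuations (SAP 5.1, 10.2).
- Mental status tables count abnormal mood and psychiatric symptoms but do not identify suicidal ideation.

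The remainder is mainly ideation below Questions 4 and 5 that the investigator neither reported as an adverse event nor acted on by withdrawal.

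**3. How much a table could show**

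There are 5 post-dose C-SSRS visits in the Treatment Period (Visits 3 to 7). With the planned 400 non-Chinese subjects, that is at most 400 × 5 = 2,000 scheduled assessments. The realised number is not given. Assuming 200 subjects and full attendance, it is 200 × 5 = 1,000.

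The two-sided 95% Clopper-Pearson upper limit for zero events in *n* subjects is 1 − 0.025^(1/*n*):

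- *n* = 100: 1 − 0.025^(1/100) = 3.6%
- *n* = 50: 1 − 0.025^(1/50) = 7.1%

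Exact power of a two-sided Fisher test at 0.05, for assumed true rates of 1% on placebo and 3% on PSL:

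| Comparison | Placebo : PSL | Power |
|---|---|---|
| Placebo vs PSL total | 100 : 300 | 7.2% |
| Placebo vs PSL total | 50 : 150 | 0.2% |
| Placebo vs one dose | 100 : 100 | 3.4% |
| Placebo vs one dose | 50 : 50 | 0.2% |

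The rates and the halved arm size are assumptions. The table would be descriptive, like the other safety tables in SAP 10.

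**The case against.** The best case against is that this is a preference. The SAP follows the protocol, the C-SSRS is not a named safety variable, and several other instruments are listed only. The more serious cases have other routes into by-arm tables. The DMC also sees safety data by treatment group under a charter that is not in the documents. What remains may be a handful of subjects, for whom a listing supplies the numerator. Most of this stands, and it limits the point to a minor improvement. It does not explain why mental status and CIWA-B earn a table and the scale for the class risk does not.

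Three stronger readings are tempting, and the documents do not support them.

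- *The SAP has two conflicting C-SSRS baselines.* SAP 10.4.4.4 says "This scale is used to assess suicidal ideation and behavior at Baseline (Visit 1), and at each subsequent study visit", while SAP 3.3.2 says "the last valid measurement before the first study medication administration will be used as the Baseline value", which would point to Visit 2, where the protocol instruction is "Obtain C-SSRS data since the last visit". But the SAP 3.3.2 rule opens by yielding to any other specification, and naming Visit 1 in 10.4.4.4 can be read as one. A listing needs no baseline in any case.
- *Screening and withdrawal respond only to Questions 4 and 5.* Exclusion criterion 6 also excludes any lifetime suicide attempt, and withdrawal criterion 10 has no C-SSRS threshold.
- *The listing covers only subjects with both ideation and behavior.* The wording permits this, but SAP 3.1 says that CRF data are in general listed in full.

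**Conclusion.** The point holds as a minor, low-cost improvement. Neither document plans a by-arm count from the C-SSRS, although it measures a named class risk and the secondary objective is comparative.

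A reader might infer that suicidality is not compared with placebo at all, or that the SAP departs from the protocol. Neither is so: reported events and withdrawals are counted by arm, and both documents plan a listing only.

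The gap is mainly lower-level ideation seen on the scale and not reported as an adverse event. Its size cannot be judged from the documents. With an assumed 50 to 100 subjects per arm, a table could show a gross imbalance but could not exclude a small one.

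**What to change.** In SAP 10.4.4.4:

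1. Add one descriptive Safety Set table, by arm and PSL total, for the 16-week Treatment Period. Show n (%) of subjects with any post-dose suicidal ideation, any suicidal behavior, and either. The denominator is subjects with at least one post-dose C-SSRS.
2. Count scheduled, early-discontinuation and unscheduled assessments on an any-time basis. A by-visit layout would lose some of them, because SAP 3.1 leaves unscheduled visits out of by-visit summaries and SAP 3.2.4 does not map early-discontinuation questionnaires.
3. Show subjects positive before dosing (Visit 1 or Visit 2) alongside. No new-onset rule is then needed.
4. Give the same counts as a separate panel for Taper and Safety Follow-up, restricted to subjects who did not enter Conversion. Placebo subjects who taper stay on placebo (Protocol Table 7-3), and SAP 10.2 already tabulates TEAEs for this period. Keep Conversion data in listings, because placebo subjects who convert receive PSL.
5. Word the listing as suicidal ideation *or* behavior.

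The cost is SAP text and one table from data already collected, or three outputs (overall, Japan, non-Japan) under SAP 16. The downside is extra unpowered output in a study that was stopped early and whose SAP amendment reduced scope.
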